9.2 Therapy (Bavituximab and Sorafenib) Treatment Parameters

Parameters for initiation of therapy (day 1) cycle #1 are as follows:

- Absolute neutrophil count $\geq 1,200$ cells/mm³
- Platelet count $\geq 70,000$ /mm³
- Hemoglobin ≥ 8.5 g/dl
- Creatinine ≤ 1.5 times upper limit of normal
- Total bilirubin ≤ 3.0 mg/dl

Parameters for subsequent cycles of therapy (cycles 2-6+) on day of or day-1 pre-therapy:

- Absolute neutrophil count $\geq 1,000$ cells/mm³
- Platelet count $\geq 50,000$ /mm³
- Total bilirubin ≤ 5.0 mg/dl

All laboratory and coagulation evaluations as listed in the screening period should be performed prior to start of each cycle.

If above parameters are not met for therapy, hold until recovered, maximum 4 weeks then re-treat per section 9.4, Dose Delays and Modifications.

9.3 Supportive Care Guidelines for Therapy (Bavituximab and Sorafenib)

- Recommended anti-emetics for therapy regimen
 - Bavituximab and sorafenib are minimal risk emetogenic regimens. The anti-emetic regimen is per institution guidelines and typically includes no additional anti-emetic therapy.
- Recommended pre-medication regimen to reduce infusion reactions
 - The recommended pre-medication regimen includes the following prior to bavituximab infusion prior to infusion:
 - Hydrocortisone 250 mg IV on all days of IV therapy
 - Diphenhydramine 50 mg IV on all days of IV therapy

The dose of hydrocortisone may be reduced or omitted where medically indicated (i.e. diabetes).

Concurrent supportive care is not restricted, including the use of narcotics for pain control, anti-emetics or anti-diarrheals. No concurrent chemotherapy, immunotherapy, radiation therapy or chemoembolization is permitted during therapy. Use of epoetin alfa and white blood cell support is permitted at the discretion of the treating physician.

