Another study in advanced solid tumor malignancies was conducted using 3 mg/kg bavituximab weekly for 8 weeks in combination with chemotherapy (docetaxel, gemcitabine, or paclitaxel + carboplatin). Two patients in the docetaxel arm discontinued bavituximab treatment after developing severe infusion reactions; urticaria in both patients. In response to these observed infusion reactions, the protocol was amended to add instructions for premedication with a steroid and an antihistamine prior to each bavituximab infusion. One patient with stage IV ovarian carcinoma developed grade 4 refractory hypotension 2 days after receiving the initial dose of docetaxel and bavituximab and expired 1 week after the initial serious adverse event (SAE); these events are considered probably study drug related. Twelve of the 14 patients enrolled were evaluable for tumor response using Response Evaluation Criteria in Solid Tumors (RECIST). Three patients achieved partial response (PR) (2 in the paclitaxel/carboplatin arm, 1 in the gemcitabine arm) and continued bavituximab maintenance on compassionate grounds, 3 patients demonstrated stable disease, and 6 patients had tumor progression. (26)

Two non-IND phase 2 studies are ongoing in locally advanced or metastatic breast cancer, to investigate the safety and efficacy of bavituximab 3 mg/kg weekly in combination with carboplatin plus paclitaxel in 28-day cycles or docetaxel in 28-day cycles. Fifteen of 46 patients treated in PPHM 0702 experienced AEs considered related to bavituximab, including fatigue and anemia, and 4 patients experienced drug-related severe adverse events (SAE);

among stage A patients (in a Simon 2-stage design) in the intent-to-treat (ITT) group, the ORR was 60% (9/15). Thirty-six of 46 patients treated in PPHM 0704 experienced AEs considered related to bavituximab, including epistaxis, infusion-related reaction, nasal dryness, and nail bed bleeding, and 4 patients experienced drug-related SAEs; the ORR for all enrolled patients was 61% (28/46). In PPHM 0702 and 0704 there were 6 grade 3 or 4 AEs (6 of 92 patients, incidence of 6.5%). The median number of bavituximab doses for a grade 3 or 4 adverse event was 15 (range, 8 to 20). (27, 28)

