5.0 THERAPEUTIC/DIAGNOSTIC AGENTS

5.1 Bavituximab

IND Number: 109134

Finished Product

Presentation and Composition

Bavituximab is supplied as a sterile, preservative-free solution with 10 mM acetate at pH 5.0 and diluted with 0.9% (w/v) saline (normal saline) to a final volume of 100 mL.

Storage

Bavituximab is stored at 2°C to 8°C. Once diluted, it should be stored at room temperature and used within 8 hours.

Availability and Accountability

Peregrine Pharmaceuticals, Inc in Tustin, CA will provide bavituximab. The pharmacist or designee must keep an accurate accounting of the number of investigational units received from Peregrine, dispensed to patients, and returned to Peregrine during and at the completion of the study. A detailed inventory must be completed for the study medication. The study medication must be dispensed only by an appropriately qualified person to patients in the study. The medication is to be used in accordance with the protocol in patients who are under the direct supervision of an investigator. All unused clinical study medications/treatments will be returned to Peregrine.

Administration

Bavituximab will be administered weekly. Prior to each bavituximab infusion, the patient must be pre-medicated with a steroid and an antihistamine to decrease the risk of an infusion reaction, 250 mg hydrocortisone IV and 50 mg diphenhydramine IV administered 30 minutes prior to infusion will be given.

Infusion preparation and administration are to be performed as follows:

1. Draw up the volume of a vial using a sterile syringe attached to an appropriate needle (a vented spike or other appropriate transfer device may be used). Fill treatment into a sterile glass bottle or plastic IV bag.
2. Using aseptic techniques, repeat procedure until the calculated volume has been put in to the container. Bring the final volume to 100 mL using 0.9% Sodium Chloride Injection, USP.
3. Administer through a low protein binding 0.2-micrometer in-line filter (placed as proximal to the patient as practical).
4. Affix the infusion line and prime it with infusate before starting the infusion. Infuse the solution intravenously over 90 (\pm 10) minutes. No reduction in infusion time will be permitted. Flush the line with normal saline after infusion.

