11.0 DOSE-LIMITING TOXICITIES-PHASE I COMPONENT

The phase I component of the study will consist of a traditional 3+3 dose escalation rule with the dose of sorafenib remaining constant and the dose of bavituximab escalating up to 3.0 mg/kg weekly to determine the maximum tolerated dose (MTD) that will be used during the phase II component. Sorafenib has been demonstrated in multiple phase I and II studies in advanced HCC to have minimal toxicity and to be safe, therefore doses will be constant. (13,14) Cohorts of three patients will be assigned to one dose level of bavituximab starting at 0.3 mg/kg weekly. Only the first cycle of therapy (4 doses of bavituximab and 4 weeks of sorafenib constitutes a cycle) will be used to determine dose limiting toxicity (DLT). The patients will be followed for thirty days following the end of the first cycle for adverse events. These adverse events will be submitted to the Data Safety Monitoring Committee for evaluation. During this thirty-day period and beyond patients will be administered sorafenib at the discretion of the treating oncologist. Patients will be enrolled into the next highest drug cohort only after 3 or 6 patients have completed the first cycle of therapy. The number of observed toxicities is counted and the traditional escalation rule applied:

- No toxicity: the next three patients will be assigned to next higher dose level (3.0 mg/kg of bavituximab is the highest dose assigned).
- At least two toxicities: the MTD is exceeded and the phase I component of the trial will be stopped with the next lowest dose to be defined as the MTD that will be used in the phase II component.
- One toxicity: the cohort will be expanded to 6 patients.
 - One DLT within the last six patients: The next cohort of three patients will be assigned to the next highest dose level
 - At least two DLTs within the last six patients: the MTD is exceeded and the phase I component of the trial will be stopped with the next lowest dose to be defined as the dose that will be used in the phase II component.

The Data and Safety Monitoring Committee and investigators as described below will regularly review all adverse events. The study will utilize the Common Terminology Criteria for Adverse Events (CTCAE) version 4.0 for grading of all adverse events related to treatment.

The following will be considered a dose-limiting toxicity:

- Grade 4 neutropenia and thrombocytopenia ≥ 7 days (absolute granulocyte count $< 0.5 \times 10^9/L$)

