- platelet count $< 25,000$
- ALT or AST levels \geq grade 3 adverse event for 7 days
- \geq grade 3 adverse event for any non-hematologic toxicity (excluding alopecia and non-premedicated nausea/vomiting) attributable to drug therapy by the definition of definite or probable and not possibly. In the SHARP trial patients in the placebo arm had over a 50% \geq grade 3 adverse event rate due to the comorbidities seen in the patient population with advanced HCC.

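### White-cell support allowed in cycle 1 can take grade 4 neutropenia out of the DLT count, which requires at least 7 days' duration; and sections 5.1 and 9.3 disagree on whether steroid premedication is mandatory

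*Combined protocol and SAP*

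**What the plan says.** **White-cell support.** Section 9.3, which covers both phases, says: "Use of epoetin alfa and white blood cell support is permitted at the discretion of the treating physician". No cycle or phase is carved out.

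**Haematologic DLT.** Section 11 takes DLTs from the first cycle only (four bavituximab doses, four weeks of sorafenib). The haematologic criterion begins "Grade 4 neutropenia and thrombocytopenia ≥ 7 days" and gives a granulocyte threshold. It does not mention growth-factor use.

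**Premedication.** Section 5.1 says that before each infusion "the patient must be pre-medicated with a steroid and an antihistamine to decrease the risk of an infusion reaction". Section 9.3 lists the same two agents at the same doses but labels the regimen as recommended, and adds: "The dose of hydrocortisone may be reduced or omitted where medically indicated (i.e. diabetes".

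**Non-haematologic DLT.** Section 11 counts any non-haematologic toxicity of grade 3 or higher, with these limits: "excluding alopecia and non-premedicated nausea/vomiting) attributable to drug therapy by the definition of definite or probable". Infusion reactions are not among the exclusions.

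**The concern.** The neutropenia criterion depends on duration, and section 9.3 permits, inside the DLT window, a treatment that can shorten duration. Two patients with the same grade 4 episode could then be scored differently because one received support. The difference runs one way: support can only remove events from the count. In a 3+3 design one patient matters. A single DLT among three expands the cohort, and a second stops escalation and sets the Phase II dose at the level below.

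The premedication point is a conflict of text. A steroid left out on medical grounds breaches section 5.1 and complies with section 9.3, so sites cannot tell whether to log a deviation. Without a record of what was given, an infusion-reaction DLT in Phase I would also be hard to interpret.

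**Working it through.** **1. The plan's own figure.** Three dose levels with 3 or 6 patients each give 3 × 3 = 9 and 3 × 6 = 18, which matches the stated 9-18. The 9 assumes that all three levels are opened. At 18 every cohort is already full.

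**2. Can a grade 4 episode drop out of the count?** Section 9.3 allows support in cycle 1, section 11 counts only cycle 1, and its criterion needs at least 7 days. No other section says how a supported patient is classified. The table in section 10 schedules blood counts at each weekly bavituximab dose, so 7 days of grade 4 would normally be shown by two successive scheduled counts. Support that lifts the second count is enough for the criterion to be missed. This takes the duration to qualify neutropenia, the natural reading since the granulocyte threshold follows it. The wording could also be read as requiring both cytopenias together; support could still break that criterion.

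**3. Size under the section 11 rule.** Let p be the chance that a patient has a counted DLT. A level is passed with 0 of 3, or with 1 of 3 followed by 0 of the next 3:

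P(escalate) = (1−p)³ + 3p(1−p)² × (1−p)³

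Let o be the rate of other DLTs and n the rate of neutropenia DLTs, taken as independent. If every event counts, p = 1 − (1−o)(1−n). If every neutropenia event is masked, p = o. Both rates are assumptions, because the documents give neither for this combination.

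Example, o = 10% and n = 1%: p = 1 − 0.90 × 0.99 = 0.109, so P = 0.891³ + 3 × 0.109 × 0.891⁵ = 0.891. Masked: p = 0.10, so P = 0.729 + 0.3 × 0.59049 = 0.906.

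| Neutropenia DLT rate n | All counted, o = 10% | All masked, o = 10% | All counted, o = 20% | All masked, o = 20% |
|---|---|---|---|---|
| 1% | 0.891 | 0.906 | 0.691 | 0.709 |
| 5% | 0.824 | 0.906 | 0.622 | 0.709 |
| 10% | 0.730 | 0.906 | 0.536 | 0.709 |

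Masking every event is the extreme case. With half masked at o = 10% and n = 10%, P(escalate) is 0.824.

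**4. Which row is plausible?** Section 3.2.4 reports grade 3 or 4 neutropenia in 4 patients of the 49-patient lung cancer study (4/49 = 8.2%). That was with carboplatin and paclitaxel, includes grade 3 and carries no duration requirement. Section 12 lists neutropenia for neither sorafenib nor bavituximab, and the only DLT in the single-agent study was a pulmonary embolism. The low rows are the more credible ones.

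**5. Premedication, side by side.** Agents and doses agree. Section 5.1 is mandatory without exception; section 9.3 is advisory with a medical exception for the steroid only. No passage says which governs. For scoring there is no gap: an attributable grade 3 or higher infusion reaction is a DLT under section 11 whether or not premedication was complete, because lack of premedication excuses nausea and vomiting only.

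**The case against.** The strongest reply is that nothing would go unseen. Blood counts are taken at each dose, section 9.1 requires a medication review at each treatment visit, and section 11 has the monitoring committee and investigators review all adverse events. With two drugs not described as markedly neutropenic, the case may never arise. Most of this stands, and it limits the point to the DLT label. It does not settle that label: section 11 makes no use of the support information, and the 3+3 count follows section 11.

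A reader might infer a large distortion of the MTD. For example, a true DLT rate of 33% with 10 points masked would raise the chance of passing from 0.434 to 0.643. The documents do not support 10 points of grade 4 neutropenia lasting a week; even the broader figure seen with chemotherapy is 8.2%.

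A reader might also infer that infusion reactions are scored differently according to premedication, or that the steroid is left to free discretion. Neither holds. Section 11 counts the reaction either way, and section 9.3 ties omission to medical indication. Nor do the documents show how much omitting the steroid raises severe reactions. Section 3.2.4 records that "Two patients in the docetaxel arm discontinued bavituximab treatment after developing severe infusion reactions", but this preceded that study's premedication instruction, so it says nothing about omitting the steroid while keeping the antihistamine. Section 12.2 reports 20-30% grade I or II reactions with antihistamines, steroids or both, below the DLT threshold.

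**Conclusion.** The point holds as two limited defects. First, sections 9.3 and 11 together let a real grade 4 neutropenia fall out of the 3+3 count, with any bias towards a higher MTD. At an assumed 10% rate of other DLTs, full masking shifts the chance of escalating by 0.015 at a 1% neutropenia DLT rate (0.906 − 0.891) and by 0.176 at 10% (0.906 − 0.730). The smaller figure is nearer to what the documents suggest. These values rest on assumed rates, independence of DLT sources and complete masking. Second, sections 5.1 and 9.3 contradict each other on whether the steroid is mandatory. That needs reconciling whatever its effect on toxicity; it is not a scoring defect in section 11.

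**What to change.** 1. Amend the DLT definition in section 11 so that grade 4 neutropenia treated with white-cell support in cycle 1 stays in the DLT count and is not removed because its duration was shortened. Do not replace such patients as non-evaluable: that would discard the toxicity, and could take Phase I beyond the stated 18.
2. Reconcile sections 5.1 and 9.3 on whether the steroid is mandatory. This review takes no position on which is right.
3. Record the premedication actually given before each Phase I dose, so that any infusion-reaction DLT can be interpreted.

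None of this prescribes a change in patient care. The cost is a few sentences, minor extra recording alongside the existing medication review, and a slightly more conservative count, since an episode that would have resolved within 7 days unaided would also be counted if support was given.

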9.4 Therapy (Bavituximab and Sorafenib) Dose Delay and Modification

Treatment may be delayed no more than 4 weeks to allow recovery from acute toxicity, i.e. if treatment ends up being held for a total of >4 weeks due to toxicity, the patient should come off study.

Dose reductions are to be made according to the system showing the greatest degree of toxicity. Toxicities will be graded according to the National Cancer Institute (NCI) Common Toxicity Criteria (CTC) Version 4.0 (<http://ctep.cancer.gov/forms/CTCAEv4.pdf>).

Management of Toxicities Specific for Sorafenib

- Dose modification for skin toxicity
 - Grade 1: Continue sorafenib and consider symptomatic treatment with topical therapy
 - Grade 2:
 - First occurrence: Continue sorafenib and consider symptomatic treatment with topical therapy
 - Second or third occurrence: Hold treatment until resolves to grade 0 or 1: resume treatment with dose reduced by one dose level (400 mg daily or 400 mg every other day)
 - Fourth occurrence: discontinue drug
 - Grade 3:
 - First or second occurrence: Hold treatment until resolves to grade 0 or 1: resume treatment with dose reduced by one dose level (400 mg daily or 400 mg every other day)
 - Third occurrence: discontinue drug

There will be no listed dose delay or modification specific for bavituximab other than those illustrated in section 14.0.

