TOTAL EXPECTED NUMBER OF PATIENTS	Phase I component- 9-18 patients Phase II component-38 patients
PRE-, DURING AND POST-THERAPY TISSUE AND SERUM COLLECTION (Phase II component only)	Serum samples will be drawn for measurement of angiogenic markers, alfa-fetoprotein and inflammatory cytokines pre, during and post therapy. When feasible core biopsies will be obtained for tissue banking for research purposes and for routine H&E staining, pre and during therapy.
STUDY DRUG FORMULATIONS	Bavituximab: supplied as a sterile, preservative-free solution with 10 mM acetate at pH 5.0 and diluted with 0.9% (w/v) saline to a final volume of 100 ml. Sorafenib: information per package insert.

ROUTE OF ADMINISTRATION	Bavituximab: Intravenous (IV) Sorafenib: Oral
DOSE REGIMEN	Bavituximab: 0.3 mg/kg, 1.0 mg/kg or 3.0 mg/kg IV over 90 minutes weekly. Sorafenib: Initial dose 200 mg PO twice daily to be escalated to the target dose of 400 mg PO twice daily Phase I: Bavituximab and sorafenib are to be given for 1 cycle or 4 weeks. Phase II: Bavituximab and sorafenib are to be continued until disease progression or toxicity.
EVALUATION CRITERIA	Primary: Phase I: safety as measured by adverse events Phase II: efficacy as measured by time to progression using RECIST Version 1.1. Secondary: Phase II: 
 1. Safety and tolerability as assessed by NCI CTC v4.0 of this regimen in the phase II setting. 2. Overall survival, response rate and progression-free survival. 3. Correlation of serum and tissue markers of angiogenesis and immune response with treatment response.
DURATION OF STUDY PERIOD	Phase I: Patients will continue study treatment until 1 cycle of therapy. Phase II: Patients will continue study treatment until disease progression or toxicity.
ANTICIPATED STUDY DATES	Planned Start Date: February 2011 Planned Recruitment Closure: February 2013 Planned End Date: February 2014

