4.2 Intervention

4.2.1 Phase I component

The following is a brief schematic of Phase I component study flow:

Patients will be eligible for enrollment on study if they have a diagnosis of HCC by at least one of the following criterion listed below:

- a. Histologically confirmed hepatocellular carcinoma
- b. Axial imaging consistent with liver cirrhosis and at least one solid liver lesion ≥ 2 cm with early enhancement and delayed enhancement washout regardless of alpha-fetoprotein (AFP) levels.
- c. AFP ≥ 400 ng/ml and evidence of at least one solid liver lesion ≥ 2 cm regardless of specific imaging characteristics.

[figure not shown]
Patients also need to have advanced disease as defined previously in section 4.1. Attending surgical oncology, hepatologists and liver transplant physicians (either surgeons or hepatologists) with expertise in the management of HCC will assess suitability of surgical resection and liver transplantation at participating sites.

All patients will initially be staged with a liver protocol MRI or CT of the abdomen. A chest CT will be done if there is a concern for intra-pulmonary metastases.

Bavituximab will be administered on a weekly schedule until completion of the phase I component of the study or the development of any of the criteria for requiring removal from the study as outlined in Section 11 of the protocol. Bavituximab will be dosed according to the timeline of the phase I and II components of the study. In the phase I component, bavituximab will be started at 0.3 mg/kg and will be escalated pending DLT to 1.0 mg/kg and 3.0 mg/kg. These doses will be given intravenously over 90 minutes starting on day 1. Sorafenib will be initially dosed at 200 mg orally twice a day and escalated to the target dose of 400 mg orally twice a day at the discretion of the treating medical oncologist. Sorafenib will be started within 3 days of the initial bavituximab

dose. At the completion of the study treatment period of one cycle sorafenib will be continued at the discretion of the treating oncologist.

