9.0 TREATMENT/INTERVENTION PLAN

9.1 Therapy (Bavituximab and Sorafenib)

All therapy must be delivered within the UT Southwestern Medical Center and affiliates, VA-North Texas, and UT Austin-Seton.

[figure not shown]
Eligible patients with advanced HCC will receive the following:

Bavituximab: Phase I: 0.3 mg/kg, 1.0 mg/kg, or 3.0 mg/kg IV over 90 minutes weekly until disease progression or completion of 1 cycle of treatment. The dose of bavituximab will be determined by the progression of the standard 3+3 dose escalation rule explained in section 11.0.

Phase II: 0.3 mg/kg, 1.0 mg/kg, or 3.0 mg/kg IV over 90 minutes weekly until disease progression or DLT. The dose of bavituximab will be determined as the MTD from the phase I component as described in section 11.0.

Sorafenib: 200 mg PO twice a day escalating to 400 mg PO twice a day at the discretion of the treating oncologist.

A cycle constitutes 4 doses of bavituximab and 4 weeks of daily sorafenib. The treatment schema is shown below for one cycle of therapy.

Patients will be seen the day of, or within one day preceding administration of and bavituximab. An interim medical history, with particular reference to toxicities, including medication review and physical examination will be conducted at each therapy treatment visit.

A therapy treatment may be moved +/- 5 days for specific administration reasons, including clinic closure for holidays. Pre-treatment laboratory values will be captured during therapy treatment.

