12.0 TOXICITIES/SIDE EFFECTS

12.1 Sorafenib

1. Cardiac ischemia and/or infarction: The incidence of cardiac ischemia/infarction was 2.7% in NexavarTM patients compared with 1.3% in the placebo group and in patients treated with renal cell carcinoma. Temporary or permanent discontinuation of NexavarTM should be considered in patients who develop cardiac ischemia and/or infarction.
2. Risk of hemorrhage: An increased risk of bleeding may occur following NexavarTM administration. In the SHARP trial, an excess of bleeding regardless of causality was not apparent and the rate of bleeding from esophageal varices was 2.4% in NexavarTM patients and 4% in placebo patients.
3. Hypertension: Blood pressure should be monitored weekly during the first 6 weeks of NexavarTM therapy and thereafter monitored and treated, if required, in accordance with standard medical practice. In the SHARP trial, hypertension was reported in approximately 9.4% of NexavarTM - treated patients and 4.3% of patients in the placebo group.
4. Dermatologic: Hand-foot skin reaction and rash represent the most common adverse reactions attributed to NexavarTM. Rash and hand-foot skin reaction are usually CTCAE Grade 1 and 2 and generally appear during the first six weeks of treatment with NexavarTM. Management of dermatologic toxicities may include topical therapies for symptomatic relief, temporary treatment interruption and/or dose modification of NexavarTM, or in severe or persistent cases, permanent discontinuation of NexavarTM.

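### Section 9.4's two sorafenib reductions for skin toxicity work only from 400 mg twice daily; from the protocol's own starting dose, one listed step cuts nothing or the second has no level left

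*Combined protocol and SAP*

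**What the plan says.** Sorafenib dosing is described in several places. The Section 1.0 summary gives "Sorafenib: Initial dose 200 mg PO twice daily to be escalated to the target dose of 400 mg PO twice daily". Section 4.2.1 says "Sorafenib will be initially dosed at 200 mg orally twice a day and escalated to the target dose", and Section 4.2.2 repeats this for phase II. Section 9.1 gives "200 mg PO twice a day escalating to 400 mg PO twice a day at the discretion of the treating oncologist". None of these sections sets a date or a criterion for the escalation.

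Section 9.4 gives the rules for sorafenib skin toxicity:

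- Grade 2: treatment continues at the first occurrence, is held and then reduced at the second and third, and stops at the fourth.
- Grade 3: "First or second occurrence: Hold treatment until resolves to grade 0 or 1", then reduction; treatment stops at the third occurrence.
- In both grades the reduction reads "resume treatment with dose reduced by one dose level (400 mg daily or 400 mg every other day").

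Section 12.1 names rash and hand-foot skin reaction as the most common reactions to sorafenib and says that they "generally appear during the first six weeks of treatment". Section 11.0 describes phase I as proceeding "with the dose of sorafenib remaining constant and the dose of bavituximab escalating up to 3.0 mg/kg weekly".

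**The concern.** The reduction rule appears to have been written for a patient already on 400 mg twice daily. Every patient begins at half that daily dose, and the protocol does not say when, or whether, a given patient moves up. No section numbers the sorafenib levels or places 200 mg twice daily among them, so one dose level has no defined meaning for a patient still on the starting dose.

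This is a safety instruction. If a listed step leaves the daily dose unchanged, a patient whose treatment was held for grade 3 skin toxicity can be restarted on the same daily dose by someone choosing an option that the protocol lists as a reduction. The same event would bring a 50% cut in a patient who had already been escalated.

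The situation is foreseeable. Section 12.1 puts these reactions mostly in the first six weeks, and phase I treatment, one four-week cycle, lies wholly inside that window.

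**Working it through.** The plan states no figure to reproduce here. The check is dose arithmetic: total daily dose = dose per administration × administrations per day.

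**Inputs**

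- Starting dose, 200 mg twice daily (Sections 1.0, 4.2.1, 4.2.2, 9.1): 2 × 200 = 400 mg/day.
- Target dose, 400 mg twice daily (same sections): 2 × 400 = 800 mg/day.
- First listed reduced level, 400 mg daily (Section 9.4): 400 mg/day.
- Second listed reduced level, 400 mg every other day (Section 9.4): 400 / 2 = 200 mg/day on average.
- Reductions ordered before discontinuation (Section 9.4): two in grade 2 (second and third occurrence) and two in grade 3 (first and second occurrence).

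**Applying two reductions from each dose**

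| Dose at onset | Order of use | After first reduction | After second reduction |
|---|---|---|---|
| 800 mg/day | as listed | 400 mg/day; (800 − 400)/800 = 50% cut | 200 mg/day; (800 − 200)/800 = 75% cut |
| 400 mg/day | as listed | 400 mg/day; (400 − 400)/400 = 0% cut | 200 mg/day; (400 − 200)/400 = 50% cut |
| 400 mg/day | every other day first | 200 mg/day; (400 − 200)/400 = 50% cut | no listed level |

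Cuts are relative to the dose at onset. The number of listed levels matches the number of ordered reductions only in the first row. From the starting dose, either the first reduction is empty or the second cannot be carried out from the list. Discontinuation does not fill the gap, because Section 9.4 reserves it for the next occurrence (third grade 3, fourth grade 2).

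**Whether another section settles it**

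- Section 5.2 refers to the package insert for product information, preparation and adverse events, but sends administration back to Sections 4.2.1 and 4.2.2, which contain the 200 mg twice-daily start.
- Section 12.1 mentions dose modification for skin toxicity but gives no levels.
- Section 14.0 gives reasons for coming off study, not dose levels.
- Section 11.0 calls the phase I sorafenib dose constant. This may mean only that sorafenib is not the drug escalated between cohorts. Read literally, it conflicts with the escalation allowed in Sections 4.2.1 and 9.1. On neither reading does it define a reduction from the starting dose.

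**The case against.** The strongest reply is that the operative instruction is to reduce. Resuming the same daily dose is not a reduction, so a sensible investigator with a patient on 400 mg/day would choose 400 mg every other day. By total daily dose, the starting dose already sits level with 400 mg daily, and the other option is one step down. This is a fair reading, and it rules out a stronger claim that a reader might infer: that the protocol requires re-exposure at an unchanged dose. It permits that but does not compel it. Even calling 400 mg daily the first step relies on word order, since the protocol does not label the levels. The reply does not rescue the rule, however, because it leaves the second ordered reduction with no listed level.

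Other provisions limit the harm. Treatment resumes only after recovery to grade 0 or 1, Section 12.1 allows interruption or permanent discontinuation in severe or persistent cases, and Section 14.0 allows removal for unacceptable toxicity or in the patient's interest. These stand as safeguards, but they do not define the reduction.

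Several further inferences are not supported:

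- **A count of affected patients.** Applying the 8% grade 3 hand-foot rate quoted in Section 3.1 to the 38 phase II patients gives 0.08 × 38 ≈ 3. That is not the affected group, which is limited to patients still unescalated at onset. The protocol gives no figure for that proportion and does not state the dose behind the 8%. Repeated grade 2 events would add to the count by an unknown number.
- **Distorted discontinuation counts.** Section 9.4 triggers discontinuation by number of occurrences, not by dose level, so any effect is indirect.
- **Differences between sites, or doses misrecorded as reduced.** Both are possible, but the documents contain no case report form and no evidence on either.
- **Bias in the primary endpoint or the dose-limiting toxicity rule.** None is shown.

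**Conclusion.** The concern holds as an internal contradiction in a stated safety rule. Section 9.4 orders two successive one-level reductions and lists two levels, which works from 800 mg/day (50%, then 75% below the dose at onset) but not from the 400 mg/day on which every patient starts. From there, the choice is a 0% cut at the first reduction or no listed level at the second.

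The conclusion rests on comparing total daily dose; Section 9.4 does not say whether 400 mg daily is taken at once or divided. It also requires that some patients have skin events before escalation. The undated escalation and the six-week window in Section 12.1 make that plausible, but its frequency cannot be estimated from the documents. The finding depends on the contradiction, not on a count.

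**What to change.** Reconcile Section 9.4 with Sections 1.0, 4.2.1, 4.2.2 and 9.1, so that the reduction instruction is consistent with the starting dose as well as the target dose at each occurrence where a reduction is ordered. In the same amendment, reconcile the description of a constant sorafenib dose in Section 11.0 with the discretionary escalation. Which levels and rules apply is for the sponsor and investigators to decide; none is proposed here.

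The cost is a short wording amendment, with no added patients or procedures and no change to the sample size.
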